6.4. Treatment allocation / Concealment of allocation

The study will be randomized, including a ratio of 2:2:1 (14:14:7 participants, in the lower dose, higher dose and placebo groups, respectively) and the allocation of treatment will be performed through a randomization list generated by the person responsible for the statistical analysis of the study.

- G1 (lowest dose) = 14 participants;
- G2 (highest dose) = 14 participants;
- G3 (placebo) = 7 participants.

The Research Center will receive the identification code of the packaging containing the investigational or placebo products to be dispensed according to the order of inclusion of the participants.

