6.5. Study blinding / Procedure for blind breakage

The study will be triple-blind, blind to the participant, the Researcher and those responsible for evaluating the parameters of efficacy and safety. The responsible for the Pharmacy of the Research Center, a component of the non-blind team, will dispense the investigational product in the center for the use of participants. The study's medications will be supplied in identical-looking packages to maintain the masking of the study. Neither the Investigator nor his study team will know which medication the participant is using. In addition, those responsible for evaluating the outcome will receive the results in a coded (hidden) way.

When necessary, for the safety and proper treatment of the participant, the Researcher may suspend the masking of the investigational product assigned to the participant, in order to define the appropriate treatment for clinical follow-up. The Investigator shall inform Sponsor of the breach of the blind code if it has not been notified previously.

Thus, if necessary, there will be the breaking of the blind code by opening the number of the medication kit from the randomization list. The reason for breaking the code must be recorded in the attendee's source document.

The professionals responsible for the analysis of the safety and efficacy parameters defined in the study will also be blind elements, as well as the *data manager* and the statistician involved.

For the accounting of the drugs used in the study, there will be a non-blind monitor designated for such function.

The pharmacist or delegated professional will also be non-blind and will administer the drugs to the research participants.

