6.6. Packaging and labelling

The statistician of the study will forward to the Sponsor and, only to the Sponsor, the sequential randomization list. Sponsor shall perform sample masking and proper product labeling, including the sequential number featured on the packaging, so that the investigational product is randomized by the Research Center which will include participants in the appropriate sequence. The head of pharmacy at the Research Center, a component of the non-blind team, will dispense the investigational product in the center for the use of the participants. Therefore, physicians and participants will not have access to the packaging of medicines.

The product under investigation will be supplied on the packaging and will be labelled with the information necessary to identify the product intended for clinical research (Figure 7).

[figure not shown]

Figure 7. Label template for products intended for research (A) Source: ANVISA; (B) Label model used for the study

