#### 7.6. Change from the Analysis Plan in Protocol

The analysis described in this SAP supersedes what was in the protocol as it was deemed more appropriate based on the data collected in the study and analysis methods for studies in Huntington's disease.

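### The protocol has the person responsible for the analysis generate the randomisation list, so its statement that the statistician is blind does not hold as written

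*Protocol*

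**What the plan says.** Three consecutive protocol sections deal with the list and the blind.

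- **6.4 (allocation).** Treatment is assigned from a "randomization list generated by the person responsible for the statistical analysis of the study". Kits are "to be dispensed according to the order of inclusion of the participants".
- **6.5 (blinding).** The trial is "blind to the participant, the Researcher and those responsible for evaluating the parameters of efficacy and safety". The section later adds: "The professionals responsible for the analysis of the safety and efficacy parameters defined in the study will also be blind elements", and extends this to the data manager and the statistician. The roles it names as non-blind are the head of pharmacy, the pharmacist or delegate who administers the product, and one monitor for drug accounting.
- **6.6 (packaging).** "The statistician of the study will forward to the Sponsor and, only to the Sponsor, the sequential randomization list". The sponsor then masks and labels the product, "including the sequential number featured on the packaging, so that the investigational product is randomized by the Research Center".

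Under Protocol 8, the tabulated study data go to the statistician responsible for the study. SAP 7.6 says the SAP analysis replaces the protocol's because it was "deemed more appropriate based on the data collected in the study" and in view of methods used in Huntington's disease studies. SAP 7.4.1 allows the primary model to be changed, or alternatives to be run, because of the small sample and visits disrupted by COVID-19.

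**The concern.** Sections 6.4 and 6.6 put the sequential list in the hands of the analysing statistician and the sponsor. Section 6.5 says the statistician and the analysts are blind. Both cannot be true, and no separate list holder or firewall within the sponsor is described.

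Blinding the analyst protects the choices made after data exist: the form of the endpoint, the contrast, the model, and any later change to them. In this trial several such choices came late. The SAP is dated 16 March 2022 and already describes the final-visit MRI in the past tense for all participants. It introduces an annual-slope endpoint, a pooled active-versus-placebo primary contrast and an MMRM, and keeps the model open. A reader of the results would want to know that whoever made these choices could not link participants to arms. The protocol offers that assurance in 6.5 and removes it in 6.4 and 6.6.

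**Working it through.** The check is mainly a comparison of sections. The only arithmetic concerns the arm sizes.

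1. **Arm sizes.** Inputs are N = 35 and the ratio 2:2:1 (Protocol 6.4). Low dose: 35 × 2/5 = 14. High dose: 35 × 2/5 = 14. Placebo: 35 × 1/5 = 7. The plan's 14/14/7 reproduces.

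2. **Could the blind statistician be a second person?** Section 6.4 identifies the list's author by function, as the person responsible for the analysis. Section 6.5 says those responsible for the efficacy and safety analysis are blind, and then adds the statistician. Even if the statistician in 6.5 is someone else, the person in 6.4 still falls in the first group. Neither the list's author nor any sponsor role is among the non-blind roles in 6.5.

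3. **Does the list reveal arms?** Yes. The trial has one centre (4.1), the sequential number is on the package (6.6), and kits go out in order of inclusion (6.4). The list plus the order of inclusion gives each participant's arm. Outcome data reach the statistician under section 8, so one role can hold both.

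4. **Would a coded list help?** Suppose, as an assumption the documents do not state, that the list showed only codes A, B and C. If nothing else were known, the chance of naming the placebo code would be 1/3. With sizes 14, 14 and 7, the placebo code is the one with 7 entries, so it is identified with certainty. Only low versus high dose stays hidden, at 1/2. The SAP's primary contrast, pooled active versus placebo (SAP 5), would still be visible to the list's author.

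5. **What remains discretionary?** The SAP fixes the pooled primary contrast (section 5), the ITT and per-protocol definitions (section 6), and the covariance structure, with a six-step ordered fallback if the model does not converge (7.4.1). Protocol 8.10 rules out interim analysis. Still open are the primary model clause in 7.4.1 and the optional analyses: responder, subgroup, and post- minus pre-treatment slope.

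6. **Do other sections repair it?** Protocol 8 has analysis follow query resolution, 8.2.3 has major violations reviewed before analysis, and 8.8.5 describes the database freeze. None ties release of arm codes to the freeze. SAP 1 says the study report will identify changes from the protocol, but not who made them or what they could see. The SAP text available does not say who held the list or when codes are released.

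7. **Scale.** Each placebo participant is 1/7 = 14.3% of the comparator. This describes how small the arm is; it is not an estimate of bias.

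**The case against.** The strongest reply is that the contradiction is narrower than it looks, and much of that reply stands.

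- **A reader might infer that the triple-blind design has failed.** The documents do not support this. Section 6.5 defines triple-blind by participant, Researcher and evaluators of efficacy and safety, and has outcome assessors receive coded results. The statistician and data manager are added afterwards. No section shows a failure among participants, investigators or raters.
- **A reader might infer that the SAP was rewritten with knowledge of the arms.** This is not shown either. No text links the list's author to the SAP's author or says allocations were used. The SAP also gives reasons unrelated to outcome by arm: analyses of other Huntington's disease studies (SAP 1 and 7.6), and sample size and COVID-19 (7.4.1). Its front pages were not available for review, so a missing role or signature there is not held against it.
- **The endpoint change is partly inherited.** Protocol 8.7.1.1.1 already models the motor score, while 3.1.1 and 8.3 name the whole UHDRS. The SAP keeps one of two versions. The slope form and the pooled contrast are new.
- **Sponsor access is not itself a fault.** The sponsor labels the product, and under Protocol 6.8 it supplies a quantity that depends on weight and treatment group. Some sponsor function must know allocation.
- **Sponsor discretion over discontinuation adds little.** Under 5.2.3(d) that discretion is shared with the blind investigator, and participants so discontinued stay in the SAP's ITT population.

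The reply does not remove the contradiction between 6.4, 6.5 and 6.6, or supply a separation between those who hold the list and those who decide the analysis.

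**Conclusion.** The stated blinding of the statistician does not hold as the protocol is written, and no other section repairs it. What is established is an unprotected exposure at the level of the statistician and the sponsor, not a bias that occurred. Its effect on the result cannot be quantified from the documents. It matters here because the placebo arm has 7 people, the primary model may still change, and the SAP partly bases its departure from the protocol on the collected data. The conclusion rests on 6.4 and 6.6 being followed as written; if another person in fact made and held the list, the fault is in the protocol text alone. It should be corrected or disclosed before results are reported.

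**What to change.** 1. Reconcile Protocol 6.4 to 6.6 so that the list is generated and held by an unblinded function with no part in analysis, enrolment or dispensing. The sponsor's labelling function, which already receives the list, is one candidate. The pharmacy is not suitable: under 6.5 its non-blind staff dispense and administer the product, so they would know upcoming assignments.
2. Limit sponsor access to that function, and name it in 6.5 among the non-blind roles.
3. State that arm codes go to the analysis team only after database freeze and SAP sign-off.
4. If the analyst already held the list, remove the statement that the statistician is blind. State in SAP 7.6 who made the slope endpoint, pooled contrast and model changes, with what access to allocation, and the SAP sign-off date relative to database freeze and code release.
5. Label any later model change as made with or without access to allocation.

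The cost is protocol and SAP wording plus, where still possible, a change of list custody. List generation needs someone outside the analysis team, which may take a little extra staff time. The SAP's past-tense account of the final MRI suggests that custody can no longer be changed for this trial. In that case steps 4 and 5, and the code-release rule if codes are still held back, are what can still be done; they require only documentation.

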6.5. Study blinding / Procedure for blind breakage

The study will be triple-blind, blind to the participant, the Researcher and those responsible for evaluating the parameters of efficacy and safety. The responsible for the Pharmacy of the Research Center, a component of the non-blind team, will dispense the investigational product in the center for the use of participants. The study's medications will be supplied in identical-looking packages to maintain the masking of the study. Neither the Investigator nor his study team will know which medication the participant is using. In addition, those responsible for evaluating the outcome will receive the results in a coded (hidden) way.

When necessary, for the safety and proper treatment of the participant, the Researcher may suspend the masking of the investigational product assigned to the participant, in order to define the appropriate treatment for clinical follow-up. The Investigator shall inform Sponsor of the breach of the blind code if it has not been notified previously.

Thus, if necessary, there will be the breaking of the blind code by opening the number of the medication kit from the randomization list. The reason for breaking the code must be recorded in the attendee's source document.

The professionals responsible for the analysis of the safety and efficacy parameters defined in the study will also be blind elements, as well as the *data manager* and the statistician involved.

For the accounting of the drugs used in the study, there will be a non-blind monitor designated for such function.

The pharmacist or delegated professional will also be non-blind and will administer the drugs to the research participants.

6.6. Packaging and labelling

The statistician of the study will forward to the Sponsor and, only to the Sponsor, the sequential randomization list. Sponsor shall perform sample masking and proper product labeling, including the sequential number featured on the packaging, so that the investigational product is randomized by the Research Center which will include participants in the appropriate sequence. The head of pharmacy at the Research Center, a component of the non-blind team, will dispense the investigational product in the center for the use of the participants. Therefore, physicians and participants will not have access to the packaging of medicines.

The product under investigation will be supplied on the packaging and will be labelled with the information necessary to identify the product intended for clinical research (Figure 7).

[figure not shown]

Figure 7. Label template for products intended for research (A) Source: ANVISA; (B) Label model used for the study

6.7. Storage and stability

The investigational product will be stored in an appropriate location on the premises of Cellavita Pesquisa Científica Ltda (Sponsor), specifically in cryopreservation (liquid nitrogen -196°C) and/or ultra-freezer (-80°C) applications with temperature and access control, until the dates on which the administrations to the research participants will occur. Since Sponsor will have the product in custody most of the time, inventories as well as storage temperature control will be monitored by Sponsor, and any deviations from requirements, including the conducts employed, shall be recorded. After identifying any deviation, Sponsor shall judge whether it was significant and/or impactful on the quality and safety of the product, keeping it under quarantine or not, until cellular feasibility tests are performed to allow its use.

On the scheduled date for the participant's hospitalization, the investigational product (ready for use according to the "Manual of presentation and instructions for administration of the Cellavita-HD product") will be forwarded to the Research Center in containers with thermal insulation transported according to the GCP, so that there is maintenance of its temperature.

6.8. Chain of custody

The investigational product will be provided by Sponsor in sufficient quantity (depending on the participant's weight and treatment group) on the scheduled date for administration. The receipt and conference of the product by the Pharmacy of the research center will be carried out by a delegated professional of the Research Center, which will include the verification of the lots, visual physical integrity and the transport temperature. After the samples have been checked and the documentation regarding entry into the company have been completed, the products will be stored properly, according to the specifications of the "Manual of presentation and instructions for administration of the Cellavita-HD product" until the moment of infusion.

All manipulation of the investigational product will be carried out in a standardized manner, in accordance with the specifications present in the "Manual of presentation and instructions for administration of the Cellavita-HD product" and in accordance with the Standard Operating Procedures (SOPs) of the research center. Handling, dispensing, disposal and/or loss (if applicable) will be recorded by the

responsible professional. The labels of the packaging used will be kept in the management record of the investigational product of each participant.

The accounting of unused products will be carried out and they will be forwarded to Sponsor for disposal procedures. The chain of custody is summarized in Figure 8.

[figure not shown]

Figure 8. Chain of custody flowchart

6.9. Concomitant medicinal products prohibited during the study

Any medicinal product administered during each administration cycle with cytotoxic/cytostatic or immunosuppressive action, such as:

- Cytotoxic/cytostatic drugs: medicinal products belonging to the groups of nitrogen mustards, alkyl sulfonates, ethylenimines, methyl melamine, nitrosoureas and triazenes, as well as folic acid analogues, pyrimidine analogues and purine analogues.
- Immunosuppressive drugs: azathioprine, tacrolimus, cyclosporine, prednisone, sodium mycophenolate, mycophenolate mofethyl, everolimus, sirolimus. In the specific case of immunosuppressive drugs, the withdrawal of the participant will be performed at the discretion of the Principal Investigator, considering the administered dose and the frequency of administration.

Other drugs that may interfere with cell viability should be evaluated on a case-by-case basis.

7. SCHEDULE OF VISITS AND PROCEDURES OF THE STUDY

7.1. Procedure for entry of Participants

7.1.1. Informed Consent Form (ICF)

The benefits and risks related to participation in the study will be explained to the participant before performing any procedures related to the study. If the participant agrees to participate in the study, the participant must sign, date and rubric in his own hand, two original copies of the ICF, as well as the Researcher and/or the person responsible for the application of the document. One of the signed copies will remain with the Investigator and the other must be delivered to the participant.

If the research participant and/or his/her legal representative are unable to read and understand, an impartial witness must be present during the discussion of consent. After reading and explaining the Informed Consent, the research participant must orally provide his/her consent, and then his/her fingerprint must be collected in the document and the witness must sign and date the Informed Consent Form at the appropriate place. Due to the motor involvement characteristic of the studied condition, some participants may have difficulty writing their signature, despite being able from a cognitive point of view. For these participants, only the fingerprint should be collected in the document.

The ICF must have been previously approved by the CEP responsible for the institution where the study will be conducted.

7.1.2. Preserving the identity of research participants

Participants will be selected according to the inclusion and exclusion criteria, consecutively (order of inclusion). After the research participant agrees to participate in the study and sign the Informed Consent, he/she will receive a code, which will identify him/her during the study. This code is composed of the initials of the first name, the middle name (if it does not exist, a dash "-") and the last name must be inserted (disregard names that refer to kinship, for example, Junior, Filho, Neto, etc.), followed by the date of birth in the format "DDMMYYYY". So, we will have the following code as the example:

[figure not shown]

Figure 9. Participant code.

The participant's code must be included in all documentation involving the participant and must accompany him/her from the beginning to the end of the study, in order to preserve his/her identity.

In case of need for breach of confidentiality of the code, this will be done by the Principal Investigator, who will have access to the confidential coding data of the participants. Code breaking, which may occur in cases of health inspection, at Sponsor's request or at the discretion of the Investigator, must be carried out with the consent of the participant and the Investigator. The breaking of the codification without the participant's consent will only be performed in case of emergency.

7.1.3. Acceptable contraceptive methods

In this study, the following contraceptive methods are generally considered reliable when used correctly: oral contraceptives, contraceptive patches, contraceptive injection, male condom, diaphragm or cervical hood with spermicide, contraceptive vaginal ring, intrauterine device, surgical sterilization (bilateral tubal connection), vasectomized partner or sexual abstinence.

The Researcher and the participant himself will decide the appropriate method of contraception that will be used during the study, which, when necessary, will be provided by Sponsor if he/she is not using any method of contraception.

7.1.4. Exams performed for inclusion of study participants

In the Visit V-3 (inclusion) the procedures described below will be performed, that corresponds to the selection exams and/or tests necessary to obtain Baseline measurements. Additional information about each procedure performed and its methodological specifications can be found in item 7.2.

A. Laboratory diagnosis for Huntington's disease (PCR), if necessary;

- B. Clinical evaluation: anthropometric data, medical history and physical examination/vital signs (with BMI value);
- C. Laboratory tests: blood count, serum sodium, serum potassium, amylase, total cholesterol and fractions (LDL, HDL and VLDL), triglycerides, coagulogram (RNI, TAP and TTPA), alkaline phosphatase, glycated hemoglobin (HbA1c), urea, uric acid, TGO (oxalacetic glutamic transaminase), TGP (pyruvic glutamic transaminase), gamma-GT (gamma glutamyl transferase), total bilirubin and fractions (direct and indirect), serum creatinine, CK (creatine kinase) and CKmB (creatine kinase mB), β -hCG urinary for women and urine I;
- D. Serology: HIV 1 and 2 (Anti-HIV-1.2), HTLV I and II, HBV (HBsAg, Anti-HBc), HCV (anti-HCV-Ab) and FTA-ABS (*Treponema pallidum*);
 - E. Physician-reported electrocardiogram (ECG);
- F. Application of the UHDRS (*Unified Huntington's Disease Rating Scale*), CIBIS and HAM-D Scales;
 - G. Evaluation of the CNS by magnetic resonance imaging of the brain.

